5.4.3 Analysis Visits for Endpoints Based on Monthly Collection

Since the actual visit for a subject may not exactly coincide with their targeted visit date, the actual visit date is mapped to the analysis visit as in [Table 5-2](#) to [Table 5-7](#).

By-visit data collected on or before the first OLTP dose date belong to DBTP. Data collected after the first OLTP dose date, not including the safety follow-up visit, belong to OLTP. Any data occurred after EOS date will not be included in the analysis except antibody data.

For by-visit summaries, if more than one visit with non-missing measurement (including the unscheduled visits, ie, CPEVENT = 'UNSCHED') fall within the same visit window, the following rules will be applied according to the order described below for selecting one visit per visit window for summary:

1. Scheduled visit will be used regardless of the distance from the target day. Unscheduled visit will only be used when there is no measurement from scheduled visit in the visit window.
2. The visit closest to the target day will be considered for analysis.
3. If two assessment dates are equidistant from the target date, the latter visit will be considered for analysis.

Table 5-2. HIT-6 and MFIQ Analysis Visit Windows

Study Period	Analysis Visit	Target Day	Visit Window (Study Day)
Double-blind Treatment Period	Day 1 (Baseline)	1	Last measurement prior or on Day 1
	Week 4 (Month 1)	29	16 to 43
	Week 8 (Month 2)	57	44 to 71
	Week 12 (Month 3)	85	72 to 99
	Week 16 (Month 4)	113	100 to 127
	Week 20 (Month 5)	141	128 to 155
	Week 24 (Month 6)	169	156 to Week 24 dose date, if available, else to 183
Open-label Treatment Period	Week 52 (Month 13)	365	352 to 379

Table 5-3. MIDAS Analysis Visit Windows

Study Period	Analysis Visit	Target Day	Visit Window (Study Day)
Double-blind Treatment Period	Day 1 (Baseline)	1	Last measurement ≤ Day 1
	Week 12 (Month 3)	85	72 to 99
	Week 24 (Month 6)	169	156 to Week 24 dose date, if available, else to 183
Open-label Treatment Period	Week 52 (Month 13)	365	352 to 379

Table 5-4. ASC-12/GAD-7/BDI-II/Sleep Questionnaire Analysis Visit Windows

Study Period	Analysis Visit	Target Day	Visit Window (Study Day)
Double-blind Treatment Period	Day 1 (Baseline)	1	Last measurement ≤ Day 1
	Week 12 (Month 3)	85	72 to 99
	Week 24 (Month 6)	169	156 to Week 24 dose date, if available, else to 183

Table 5-5. PGIC Analysis Visit Windows

Study Period	Analysis Visit	Target Day	Visit Window (Study Day)
Double-blind Treatment Period	Week 24 (Month 6)	169	156 to Week 24 dose date, if available, else to 183

Table 5-6. HRU Questionnaire Analysis Visit Windows

Study Period	Analysis Visit	Target Day	Visit Window (Study Day)
Double-blind Treatment Period	Day 1 (Baseline)	1	Last measurement ≤ Day 1
	Week 24 (Month 6)	-	2 to Week 24/ET visit date, if available, else to 183

Table 5-7. Vital Signs Analysis Visit Windows

Study Period	Analysis Visit	Target Day	Visit Window (Study Day)
Double-blind Treatment Period	Day 1 (Baseline)	1	Last measurement ≤ Day 1
	Week 4 (Month 1)	29	16 to 43
	Week 8 (Month 2)	57	44 to 71
	Week 12 (Month 3)	85	72 to 99
	Week 16 (Month 4)	113	100 to 127
	Week 20 (Month 5)	141	128 to 155
	Week 24 (Month 6)	169	156 to Week 24 dose date, if available, else to 183
Open-label Treatment Period	Week 40 (Month 10)	281	268 to 295
	Week 52 (Month 13)	365	352 to 379

5.5 Subject Disposition

Randomized

Individuals are considered randomized if they have been assigned a randomization number. Randomized individuals are referred to as “subjects”.

On-study

Subjects are considered on-study if they have been randomized and have not yet had their end of study visit.

Exposed to Investigational Product

Subjects are defined as exposed if they receive at least one dose of investigational product.

Completing the Double-blind Investigational Product

Subjects are defined as completing double-blind investigational product if the primary reason for ending IP on End of IP DBTP eCRF is “Completed”.

Completing the Double-blind Treatment Period

Subjects are defined as completing the DBTP if they complete week-24 assessment. It will be derived from the End of Double-Blind eCRF page with “Completed” as the primary reason for ending study period.

Completing the Open-label Investigational Product

Subjects are defined as completing open-label investigational product if the primary reason for ending IP on End of IP OLTP eCRF is “Completed”.

Completing the Open-label Treatment Period

Subjects are defined as completing the OLTP if they complete the week-52 assessment. It will be derived from the End of Open-Label eCRF page with “Completed” as the primary reason for ending study period.

Completing Study

Subjects are defined as completing study if they complete the entire 52 weeks of study evaluation. It will be derived from the End of Study eCRF page with “Completed” as the primary reason for ending study.

5.6 Arithmetic Calculations

Duration of Migraine

The number of years from the diagnosis date (DXDT) of migraine (migraine with aura or migraine without aura, whichever is earlier) to the date informed consent is signed.

Observed Portion	Missing Portion	Duration of Migraine (Years)
Year, Month, Day	NA	$(\text{Informed Consent Date} - \text{DXDT}) / 365.25$
Year, Month	Day	$[\text{Year}(\text{Informed Consent Date}) - \text{Year}(\text{DXDT})] + [\text{Month}(\text{Informed Consent Date}) - \text{Month}(\text{DXDT})] / 12^a$
Year	Month, Day	$[\text{Year}(\text{Informed Consent Date}) - \text{Year}(\text{DXDT})]^a$

^a If it equals 0, add 1/12 years (ie, 1 month) to avoid a disease duration of 0.

Duration of DB IP Exposure

If subject enters into OL treatment period,

Duration = Minimum (Last DB Dose Date + 27, First OL Dose Date - 1) – First DB Dose Date + 1

Otherwise,

Minimum (Last DB Dose Date + 27, EOS Date) – First DB Dose Date + 1

Duration of OL IP Exposure

Minimum (Last OL Dose Date + 27, EOS Date) – First OL Dose Date + 1

Change From Baseline

Postbaseline monthly value – Baseline, as defined in [Section 5.4](#). If the baseline or postbaseline value is missing, the change from baseline value will be set to missing.

Percent Change From Baseline

The change from baseline divided by baseline and multiplied by 100:

$$(\text{Postbaseline} - \text{Baseline}) * 100 / \text{Baseline}$$

If the baseline value is 0 and the postbaseline value is also 0, the percent change from baseline is set to 0. If the baseline value is 0 and the postbaseline value is non-zero, the percent change from baseline is set to missing.

Mean Monthly Change From Baseline Over Multiple Months

Arithmetic mean of the observed monthly change from baseline values for the months with non-missing change from baseline values

Subject Incidence

The subject incidence for a given event in a given period is defined as the number of subjects with at least one reported occurrence of the event divided by the number of subjects who entered that period (ie, number of at-risk subjects). For subjects with multiple occurrences of the same event in a given period, the event will only be counted once per subject in that period.

Exposure-adjusted Incidence Rate

The exposure-adjusted incidence rate for a given event in a given period is defined as the number of subjects with at least one reported occurrence of the event in a given period divided by total exposure time of all subjects who are at risk for the event. For subjects with a given event, only the time until the onset of each subject's first event contributes to the exposure time. For subjects without a given event, the exposure time is the entire duration of the period. This incidence rate will be presented as number of subjects per 100 subject-years.

5.7 Disease Characteristics

Treatment Failure of Prior Migraine Preventive Medications

Treatment failure of prior preventative medications is determined by "Reason for stopping" as "Lack of Efficacy", "Adverse Reaction" or "Intolerance" on the Prior Migraine Prophylactic Medication eCRF.

6. Analysis Sets

Each analysis set will be defined separately for the non-opioid-treated cohort and the opioid-treated cohort.

6.1 Full Analysis Set

The full analysis set (FAS) consists of all subjects who were randomized in the study. Subjects will be analyzed according to their randomized treatment, regardless of the treatment received. Tabulations of demographic and baseline characteristics, disposition, and important protocol deviations (IPD) will utilize this analysis set.

6.2 Efficacy Analysis Set

The efficacy analysis set (EAS) for **all** efficacy endpoints during DBTP is a subset of FAS consisting of subjects who receive at least 1 dose of investigational product during DBTP. The respective EAS will be used to perform the analyses for the efficacy endpoints of interest during DBTP. Subjects will be analyzed according to their randomized treatment in DBTP, regardless of the treatment received.

6.3 Safety Analysis

The safety analysis set (SAS) will consist of all randomized subjects who received at least 1 dose of investigational product. Subjects will be analyzed according to the randomized treatment unless a subject receives the incorrect dose during the entire DBTP. Analysis for safety endpoints and summary of investigational product administration will utilize this analysis set.

6.4 Open-label Treatment Period Analysis Set

The open-label analysis set (OLAS) will consist of all subjects who receive at least 1 dose of erenumab in the OLTP. This analysis set will be used to summarize data collected during the OLTP.

7. Planned Analyses

Data will be subject to ongoing checks for integrity, completeness and accuracy in accordance with the Data Management Plan with the expectation that outstanding data issues are resolved ahead of the lock to the extent possible for the primary analysis and all outstanding data issues are resolved ahead of the final lock. The data supporting the primary analysis will be locked to prevent further changes.

7.1 Primary Analysis

The primary analysis will be performed when all randomized subjects in the nonopioid-treated cohort have completed the week 24/ET assessments during the DBTP, and all data are collected for the primary endpoint. All available data up to and including the data cutoff date will be cleaned and locked. At **the time of primary**

analysis, the DBTP treatment assignment for this cohort will be unblinded to selected staff of the sponsor conducting the analysis. If data collection for all subjects in the opioid-treated cohort for the DBTP is also complete, the DBTP treatment assignment for this cohort will also be unblinded. Study subjects, investigators, and remaining sponsor staff will remain blinded to original DBTP treatment assignment until study completion. All efficacy analyses and safety analyses will be conducted for the DBTP. Safety data collected during the OLTP before the data cutoff date for the primary analysis will also be summarized.

7.2 Final Analysis

The final analysis will be performed after all subjects (nonopioid-treated and opioid-treated) have completed the **study through** the week-52/EOS visit. The final analysis will be performed based on the final cleaned and locked data.

8. Data Screening and Acceptance

8.1 General Principles

The objective of the data screening is to assess the quantity, quality, and statistical characteristics of the data relative to the requirements of the planned analyses.

8.2 Data Handling and Electronic Transfer of Data

The Amgen Global Study Operations-Data Management (GSO-DM) department will provide all data to be used in the planned analyses. This study will use the RAVE database as well as eDiary data outside of RAVE database.

8.3 Handling of Missing and Incomplete Data

Subjects may miss specific data points for a variety of reasons. In general, data could be missing due to a subject's early withdrawal from the study, a missed visit, or inability to evaluate an endpoint at a particular point in time. For this study, efficacy endpoints are clinical outcome assessments (COAs) collected via daily eDiary or monthly assessments at the office visits. Missing COAs with respect to quality-of-life questionnaires (MPFID, HIT-6, MFIQ, MIDAS, Sleep questionnaire, Allodynia symptom checklist, BDI-II, GAD-7 and PGIC) will not be imputed. **Missing items in each eCOA questionnaire will be handled based on the scoring algorithm for each COA.**

Subjects could miss entering several days of data in eDiary within each monthly interval. The calculation of monthly measurements about subjects' migraine and non-migraine headaches will be handled using the following method, also described in [Section 5.1.1](#).

- For each monthly interval with ≥ 14 days of eDiary use:

- Monthly frequency measurements will be prorated to 28-day equivalents. Prorated result does not need to be rounded.
- Monthly average scores will be calculated as the average of observed scores.
- For monthly intervals with < 14 days of eDiary use, all monthly measurements will be set as missing.

Missing safety endpoints will not be imputed **except for partial AE start dates**. Missing or incomplete dates will be listed as reported, except for incomplete start date of an AE or concomitant medication, which will be imputed as follows:

Missing	Imputation	Exception on adverse event start date
Day	01	Default to study day 1 if an adverse event started the same year and month as study day 1 and the flag indicates that the adverse event started on or after the first dose of investigational product on the Events eCRF
Day/Month	01 Jan	Default to study day 1 if an adverse event started the same year as study day 1 and the flag indicates that the adverse event started on or after the first dose of investigational product on the Events eCRF
Day/Month/Year	None	—

Similarly, incomplete dates of HRU will be imputed using the same imputation rule as above.

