10.2.4.1 Missing and Incomplete Dates

Missing or incomplete dates will be listed as reported, except for incomplete start date of an AE or concomitant medication, which will be imputed as follows:

Missing	Imputation	Exception
Day	01	Default to study day 1 if an adverse event started the same year and month as study day 1 and the flag indicates that the adverse event started on or after the first dose of investigational product on the Events eCRF
Day/Month	01 Jan	Default to study day 1 if an adverse event started the same year as study day 1 and the flag indicates that the adverse event started on or after the first dose of investigational product on the Events eCRF
Day/Month/Year	None	—

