5.4 Study Time Intervals

5.4.1 Study Periods

The following data will be categorized into treatment periods. Any data occurred after EOS date will not be included in the analysis.

Efficacy Assessments at Scheduled Visits, Vitals

- DBTP: Study Day 1 to minimum (first OL dose date, EOS date)
- OLTP: (First OL dose date + 1) to EOS date

Adverse Events, Concomitant Medications

- DBTP: Study Day 1 to minimum (first OL dose date – 1, EOS date)
- OLTP: First OL dose date to EOS date

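### Partial adverse-event start dates have no guard at the first open-label dose, so some open-label events are dated into the double-blind period and, for former placebo subjects, count under placebo

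*SAP*

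**What the plan says.** SAP section 8.3 lists dates as reported, "except for incomplete start date of an AE or concomitant medication, which will be imputed as follows": a missing day becomes 01, a missing day and month become 01 Jan, and a fully missing date is left alone. The exception column is headed "Exception on adverse event start date". For a missing day it reads "Default to study day 1 if an adverse event started the same year and month as study day 1 and the flag indicates" onset on or after the first dose of investigational product. For a missing day and month it reads "Default to study day 1 if an adverse event started the same year as study day 1 and the flag indicates" the same. Protocol section 10.2.4.1 has the same table ("Default to study day 1 if an adverse event started the same year and month as study day 1").

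SAP section 5.4.1 splits adverse events and concomitant medications by date. The DBTP ends the day before the first open-label dose, and the next line is "OLTP: First OL dose date to EOS date".

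SAP section 6.3 analyses safety by randomized treatment, unless the wrong dose was received throughout the DBTP. SAP section 3.1 moves placebo subjects to erenumab 70 mg or 140 mg in the OLTP.

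On HRU, SAP section 8.3 adds: "Similarly, incomplete dates of HRU will be imputed using the same imputation rule as above".

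**The concern.** Taking the earliest date compatible with a partial record can carry an event back across a period boundary. The plan recognizes this at study day 1 and protects that boundary for adverse events. It does not protect the second boundary, the first open-label dose, which is where placebo subjects start erenumab and where the device changes from prefilled syringe to autoinjector. The only timing flag the SAP describes on the Events eCRF (section 5.1.3) refers to the first dose of investigational product, so it cannot separate double-blind from open-label onset.

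The movement is one-way, from OLTP to DBTP. For a former placebo subject it credits an event on erenumab to placebo. For a subject on erenumab throughout, the treatment is unchanged but the period is wrong. The exposure-adjusted rates (SAP sections 5.6 and 9.6.2) are affected too. A moved event enters the DBTP numerator and shortens that subject's DBTP time at risk, to about one day if it is set to study day 1. It also leaves the OLTP numerator.

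Concomitant medications share the imputation and the date split, and have no study-day-1 exception.

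**Working it through.** The plan states no figure on this point, so there is nothing to reproduce. The check traces the rule and then sizes it under stated assumptions.

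**Worked example.** Placebo subject; study day 1 = 3 March 2021; first open-label dose = study day 169 = 18 August 2021; true onset 23 August 2021, on open-label erenumab.

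| Recorded date | Imputed date | Why | Period | Column |
|---|---|---|---|---|
| 23 Aug 2021 | none needed | complete | OLTP | erenumab |
| Aug 2021 | 1 Aug 2021 | not the month of day 1, so 01 applies | DBTP | placebo |
| 2021 | 3 Mar 2021 | same year as day 1, flag set, so study day 1 | DBTP | placebo |

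**Assumptions for the size.** First open-label dose on study day 169, end of study on day 365, onset uniform over those 197 days, and the dose date uniform over a 365-day year. The denominator is 365 × 197 = 71,905 combinations of dose date and onset date.

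**Day missing.** The event moves if onset is in the calendar month of the open-label dose, unless that dose was on the 1st. For a month of L days there are L(L+1)/2 pairs of dose and later-or-same-day onset.
- Year total: 7 × 496 + 4 × 465 + 406 = 5,738.
- Less pairs with the dose on the 1st (365): 5,373.
- Share: 5,373 / 71,905 = 7.5%. Without removing doses on the 1st, 5,738 / 71,905 = 8.0%, so 7.5 to 8% covers the choice of convention.
- Within the calendar month of the dose, 5,373 / 5,738 = 93.6% move.

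**Day and month missing.** The event moves if onset is in the calendar year of the open-label dose, unless that dose was on 1 January. If that is also the year of study day 1, the date becomes study day 1. If not, it becomes 1 January, which then lies inside the DBTP. With r days left in the year, min(r, 197) onset days qualify.
- r = 1 to 197: 197 × 198 / 2 = 19,503.
- r = 198 to 365: 168 × 197 = 33,096.
- Less a dose on 1 January: 197.
- Share: (19,503 + 33,096 − 197) / 71,905 = 52,402 / 71,905 = 72.9%.

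A day-by-day enumeration over a four-year calendar cycle gives the same values: 7.5%, 93.6% and 72.9%.

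**Existing guard.** In the same enumeration, 0% of DBTP events flagged as on or after first dose leave the DBTP. The study-day-1 exception works at its own boundary; the gap is only at the later one.

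**The case against.** **The effect is small.** The 73% needs both day and month missing. Adverse events are reviewed about every 4 weeks in both periods, investigators must record onset dates, and data issues are to be resolved before lock. A missing month should be uncommon, and a missing day matters only in one calendar month per subject. This stands. It limits the size but does not remove the misassignment.

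**The rule is the same in every arm and nothing is tested.** Erenumab columns gain events as well, and SAP section 9.6.1 rules out statistical testing of safety between groups. This also stands. But only in the placebo column does a moved event change treatment as well as period.

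**Dates are not always moved back.** Correct: fully missing dates are not imputed, and flagged events sharing the month or year of day 1 go to study day 1. Neither feature protects the open-label boundary.

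**The tempting stronger reading is on HRU.** Because "incomplete dates of HRU will be imputed using the same imputation rule as above", a reader might infer that encounters reported at week 24 are dated before day 1 and so lost from the DBTP occurrence endpoints. The documents do not support that. SAP section 5.4.3 maps visit dates to analysis visits through Table 5-6. There are only two questionnaires: day 1 looks back over the prior 24 weeks, and week 24/ET looks back to day 1. Nowhere is an imputed encounter date said to decide DBTP membership. Nor would imputing to study day 1 be a remedy on that reading, since the post-baseline window in Table 5-6 starts at day 2. What remains is that the SAP does not say what the imputed HRU date is used for.

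**Conclusion.** The gap holds for adverse events and concomitant medications. It follows from sections 8.3 and 5.4.1 read together, and no other section corrects it. Among OLTP adverse events, about 7.5 to 8% of those with the day missing and about 73% of those with day and month missing would be placed in the DBTP. These shares assume uniform timing and apply only to partial dates. The documents do not say how many there are; probably few. No efficacy result is touched; the effect is confined to descriptive safety summaries. It is a minor point, worth settling because the unprotected boundary is the one where placebo subjects change treatment. For HRU no loss of events is shown; only a clarification is due.

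**What to change.** Add to SAP section 8.3:

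1. For subjects who entered the OLTP, impute a partial adverse-event start date to the first OLTP dose date when three conditions hold: the known part is compatible with that date; the event was not reported at or before the week 24 visit; and it has no stop date before that dose. This takes precedence over the study-day-1 default. Name the variable that shows when the event was first reported, since the SAP defines none.
2. Apply the same guard to concomitant medications.
3. Assign HRU encounters to baseline or DBTP by the questionnaire on which they were recorded (day 1 or week 24/ET), not by an imputed date.

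Because the protocol carries the same imputation table, list the change in SAP section 10.

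The cost is a few lines of SAP text and a small programming change. The downside is that a few true DBTP events with partial dates, first reported after week 24, may be counted in the OLTP.

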8.3.1 Missing Baseline Evaluation

Missing baseline evaluations will not be imputed.

All subjects included in the efficacy analysis set will have baseline monthly rate or monthly average of migraine and non-migraine headaches related measurements after applying proration rule defined in [Section 5.1.1](#) since only subject with $\geq 80\%$ compliance of eDiary use during baseline will be eligible for randomization.

8.3.2 Missing Post-baseline Evaluation in Double-blind Treatment Period

Primary analysis of dichotomous efficacy endpoints during the DBTP will be conducted using Cochran-Mantel-Haenszel test (CMH) after the missing data are imputed as nonresponse. Primary analysis of continuous efficacy endpoints during the DBTP will be conducted using the repeated measures linear mixed effects model including observed data without imputation.

For the descriptive summary of mean monthly value calculated using the monthly value from each of months 4, 5, and 6 (**week 13 through 24**) of the DBTP, if a subject has at least one monthly value at months 4, 5, and 6 (**week 13 through 24**), then the subject contributes to the summary statistics.

If the proportion of missing data in primary endpoint is high (eg, > 20% for primary analysis at week 24), further analysis will be performed to

- examine the frequency and reason of missing data
- determine if there are any patterns in the missing data
- distinguish true missing values from other unknown values (eg, due to measurement or sample processing error)

